9.5 Study Size

Sample size calculation is based on the second part of the primary objective, especially on predicting exacerbations of a severe or moderate type as outcome.

Assuming a desirable sensitivity and specificity of 0.85 for our algorithm and requiring that the lower 95% confidence limit should be at least 0.50 (with a probability of 0.95) for this exploratory approach, the number of observed exacerbation events needed is 18 ([Flahault 2005](#)).

Assuming that patients with COPD within our eligibility criteria (GOLD stage II-IV with a history of at least 2 moderate and/or severe exacerbations within any 12 month period within the last 3 years and at least 1 moderate or severe exacerbation within the last 12 months) show a frequency of 2 moderate or severe exacerbations per year, participants with COPD will have 0.5 events in 3 months (the in-study time). Further assuming that event occurrence over 3 months for every individual participant follows a Poisson distribution with parameter $\lambda = 0.5$, the number of events in the overall study population is also Poisson distributed and the corresponding parameter is the sum of individual parameters λ . Calculations show that a λ of 30 is needed to reach an upper cumulative distribution probability of 0.99 for observing at least 18 exacerbations. Therefore, 60 participants are needed to observe at least 18 exacerbation events within the 3-month observation period.

The events of interest in the context of the present study are COPD exacerbations (severe or moderate), exactly the onset of an exacerbation. For building the binary classifier predictive models we also require “no exacerbation” events. We will sample such events randomly from periods with no exacerbations, avoiding 2 weeks before and after an exacerbation.

Considering a drop-out rate of 10%, the estimated number is 67 participants with COPD that need to be included in this study.

This recruitment number is also in good agreement with published studies with regards to the ability to build predictive models for exacerbations. Studies with similar recruitment numbers ([Yañez 2012](#)) have been able to predict exacerbations based on single parameters studied. Strong features can compensate for low numbers in COPD machine learning model building as shown in

[Al Rajeh 2020](#), and using several features improves the accuracy of predictive models as seen in [Jensen 2012](#).

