### 1.3.2 Study size

Sample size calculation is based on the second part of the primary objective, especially on predicting exacerbations of a severe or moderate type as outcome.

Assuming a desirable sensitivity and specificity of 0.85 for our algorithm and requiring that the lower 95% confidence limit should be at least 0.50 (with a probability of 0.95) for this exploratory approach, the number of observed exacerbation events needed is 18 (1).

Assuming that COPD patients within our eligibility criteria (GOLD stage II-IV with a history of at least 2 moderate to severe exacerbations within any 12 month period within the last 3 years and at least 1 exacerbation within the last 12 months) show a frequency of 2 moderate or severe exacerbations per year, COPD participants will have 0.5 events in 3 months (the in-study time). Further assuming that event occurrence over 3 months for every individual participant follows a Poisson distribution with parameter  $\lambda = 0.5$ , the number of events in the overall study population is also Poisson distributed and the corresponding parameter is the sum of individual parameters  $\lambda$ . Calculations show that a  $\lambda$  of 30 is needed to reach an upper cumulative distribution probability of 0.99 for observing at least 18 exacerbations. Therefore, 60 participants are needed to observe at least 18 exacerbation events within the 3-month observation period.

The events of interest in the context of the present study are COPD exacerbations (severe or moderate), exactly the onset of an exacerbation. For building the binary classifier predictive models we also require “no exacerbation” events. We will sample such events randomly from periods with no exacerbations, avoiding 2 weeks before and after an exacerbation.

Considering a drop-out rate of 10%, the estimated number is 67 COPD participants that need to be included in this study.

This recruitment number is also in good agreement with published studies with regards to the ability to build predictive models for exacerbations. Studies with similar recruitment numbers (2) have been able to predict exacerbations based on single parameters studied. Strong features can compensate for low numbers in COPD machine learning model building as shown in (3), and using several features improves the accuracy of predictive models as seen in Jensen 2012.

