#### 3.4.2 Considerations for potential confounders and effect modifiers

Not applicable. All available features will be considered in the predictive modelling.

For objective 4, smoking status, and other relevant baseline covariates will be forced into the models.

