Different machine learning algorithms will be evaluated, and their performance will be assessed by estimating their accuracy, specificity, sensitivity, and area under ROC metrics. Other usual evaluation metrics such as precision, positive predictive value (PPV), negative predictive value (NPV), F1-score will be computed.

This analysis will be performed on the COPD cohort. Internal cross-validation will be tested.

The following models will be used:

- Logistic regression
- Random Forest
- K-nearest neighbors
- Boosting methods (e.g., Gradient boosting machine, GBM)
- Support vector machines (SVM)

Other methods may be tested.

The development of those models will be based on the machine learning algorithms implementation of scikit-learn (12), a python package designed for predictive data analysis. Other packages may be considered if needed (e.g., H2O (13)).

To optimize the performance of the models, feature extraction and selection algorithms will be used.

Explanatory models will be built on top of the selected machine learning algorithm (14), as a way to support rationalization for physicians and regulatory organizations. Depending on the selected ML model selected, either model specific (for logistic regression, decision trees, k-nearest neighbors) or model agnostic methods will be considered (global methods as PDP, ALE, functional decomposition, and local methods as LIME and Shapley values).

### 3.4.5.3 Secondary Objective 3

Objective 3 will be analyzed on the COPD cohort. For each pair of variables and outcomes ( $x, y$ ) defined below, Pearson's correlation coefficient will be computed together with a 95% asymptotic confidence interval based on Fisher's Z transform.

In case of low variability in parameter values (e.g., exacerbation count), parameters may be treated as ordinal and analyzed in terms of Kendall's Tau statistic with non-parametric confidence interval (see (15)).

The following variable groups and outcomes will be paired and assessed at the indicated time points:

Group x	Group y	Time points for assessment
Sensor data (see section 2.1.4), daily averages (17 variables): physical activity, heart rate, resting heart rate, heart rate variability, temperature, respiration rate, ratio of in- vs expiration time, cough frequency, sleep pattern (hours of sleep)	CAT summary score: Self-assessed patient's health status by CAT questionnaire.	Baseline (Day 0), End of study visit

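### The primary prediction model is validated only by an unspecified internal cross-validation, so the reported performance of the selected algorithm will be optimistic

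*SAP*

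**What the plan says.** SAP 3.4.5.2 (Primary Objective 2) gives validation one sentence: "Internal cross-validation will be tested". It does not state the number of folds, whether days or participants are split, whether selection is nested, how the algorithm is chosen, or how uncertainty in the metrics is expressed.

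The same section makes several data-driven choices:

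- Features: "To optimize the performance of the models, feature extraction and selection algorithms will be used". SAP 3.4.2 sets no limit on the candidates: "All available features will be considered in the predictive modelling".
- Algorithms: five families are named, and the list stays open: "Other methods may be tested".
- Comparison: "Different machine learning algorithms will be evaluated, and their performance will be assessed by estimating their accuracy, specificity, sensitivity, and area under ROC metrics".
- A winner: "Explanatory models will be built on top of the selected machine learning algorithm".

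Protocol 9.7.2.1 lists the algorithms and metrics, says the methods are meant to give unbiased models, and does not mention cross-validation. The sensitivity analyses in SAP 3.4.4 and 3.4.6 concern missing data only.

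Sample size (Protocol 9.5, SAP 1.3.2) starts from "Assuming a desirable sensitivity and specificity of 0.85 for our algorithm", with the condition "requiring that the lower 95% confidence limit should be at least 0.50 (with a probability of 0.95". Non-event days are to be drawn at random outside exacerbation periods, avoiding two weeks on either side (Protocol 9.5, SAP 2.3.1).

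**The concern.** When features or algorithms are chosen using the same outcomes that later score the model, the score partly reflects the choice itself. With few events and many candidates this can produce a respectable AUC from noise. A second route is specific to these data: one participant contributes several days, so a day-level split can put the same person in both training and test folds.

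Sensitivity, specificity and AUC are the main results for a primary objective, and sensitivity drives the sample size. The models are meant as a basis for a future monitoring solution (Protocol section 7), so an apparent signal that is not real could misdirect that work. The plan leaves open whether its figures will estimate performance in participants the model has not seen.

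**Working it through.** **1. The plan's own figures.** With a one-sided exact 95% lower limit, 18 events require at least 13 correct (limit at 13/18 = 0.502). P(X ≥ 13 | n = 18, p = 0.85) = 0.958, so 18 reproduces. The documents do not state sidedness; a two-sided interval gives 0.879 at n = 18. That is a separate matter. A Poisson mean of 60 × 0.5 = 30 gives P(≥ 18) = 0.993, and 60/0.9 = 66.7, hence 67. The sizing arithmetic holds, but it treats sensitivity as a simple proportion of independent events, with no allowance for selection.

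**2. Information available.** Expected events are 30. Participants with at least one event: 60 × (1 − e^−0.5) = 23.6, about 24, consistent with the roughly 40% in Protocol 9.9. SAP 3.4.5.3 counts 17 sensor, 13 lung-function and 20 laboratory variables, 50 in all, before app, demographic and history variables.

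**3. Selection with no true signal.** Assumptions: independent standard-normal features unrelated to outcome, independent instances, 5 folds, 150 runs per scenario, top features kept by t-statistic, and simple stand-ins for the five named families. Event numbers are the plan's minimum (18) and expectation (30). Non-event days, candidate features and features kept are assumed.

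| Events / non-events; features → kept | Selected once on all data, best of five: AUC; P(AUC ≥ 0.70); sensitivity at 0.85 specificity | Selected inside folds, best of five: same measures | Fully nested: AUC |
|---|---|---|---|
| 18 / 18; 17 → 5 | 0.717; 0.55; 0.44 | 0.569; 0.13; 0.26 | 0.500 |
| 18 / 18; 60 → 10 | 0.834; 0.94; 0.66 | 0.574; 0.15; 0.26 | 0.497 |
| 18 / 60; 60 → 10 | 0.781; 0.88; 0.54 | not run | 0.496 |
| 30 / 30; 17 → 5 | 0.670; 0.31; 0.36 | not run | 0.503 |
| 30 / 30; 60 → 10 | 0.773; 0.89; 0.53 | 0.551; 0.06; 0.22 | 0.516 |
| 30 / 60; 60 → 10 | 0.741; 0.80; 0.46 | not run | 0.507 |
| 30 / 120; 60 → 10 | 0.723; 0.67; 0.43 | 0.543; 0.01; 0.18 | 0.496 |

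Chance values are AUC 0.50 and, at 0.85 specificity, sensitivity 0.15. Monte Carlo standard errors of the nested AUC are 0.006–0.011. Choosing the best of five alone adds about 0.04–0.07 to AUC; most of the inflation comes from selecting features outside the folds. Nesting both choices removes it.

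**4. Splitting by day or by participant.** Under the random sampling rule, a participant with an exacerbation has fewer eligible days and supplies fewer controls. Features that identify the participant then carry outcome information, which a day-level split lets the model use. This was simulated with no within-patient signal and no feature selection. Assumptions: 60 participants, at least 18 events, 38 days excluded per event, 20 fixed participant-level features, 17 daily features with intraclass correlation 0.5, 30–120 controls, nearest-neighbour and ridge classifiers, 200 runs per setting.

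- Day-level folds, equal risk: mean AUC 0.56–0.61.
- Day-level folds, gamma-distributed risk (shape 1 or 0.5): 0.63–0.75.
- Participant-grouped folds: 0.46–0.52.

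A separate simulation of the same rule gave 0.51–0.62 by day and 0.47–0.51 grouped. When every participant instead supplied a fixed 1 or 3 control days at equal risk (intraclass correlation 0.5), day-level splitting did not inflate AUC (0.454 and 0.500). The mechanism therefore depends on how controls are drawn and how unequal risk is.

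**The case against.** The strongest reply is that this is an exploratory study. Protocol section 7 says any model will need validation in future studies, and Protocol 9.9 says events will be few and models must be refined in a larger population. This stands as a reason for lower severity. It does not make the sensitivity and AUC reported here unbiased.

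A reader might infer more than the documents support:

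- *That features will be selected on all data.* The SAP does not say so. The 0.67–0.83 range describes a procedure left open. With selection inside the folds, only the smaller optimism from choosing an algorithm remains.
- *That a model with no signal would typically reach the target.* The planning values are 0.85 for both sensitivity and specificity. Even with selection outside the folds, mean null sensitivity at 0.85 specificity is 0.36–0.66: well above chance, but short of the target.
- *That the lack of a held-out set is a defect.* With 18 to 30 events a hold-out would tell little.
- *That the cough, activity and sleep classifiers leak the outcome.* SAP 3.4.3 trains them on app labels and self-reported bedtimes, not on exacerbation status. No effect on exacerbation performance has been shown.
- *That a planned confidence limit is invalid.* SAP 3.4.5.2 plans none for sensitivity; 0.50 is a sizing input.

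It is also fair to say that day-level splitting does not always inflate AUC, as the fixed-control runs show. The grouping argument rests on the plan's random sampling of control days.

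**Conclusion.** The point holds as a consequential gap in the plan for a primary objective. Choosing among five or more algorithms on the same cross-validation that is then reported is optimistic even when features are handled correctly. If features are chosen once on all data, noise alone reaches an AUC of 0.70 in 31%–94% of simulated datasets, compared with 1%–15% when they are chosen inside the folds. Day-level folds are a further, less certain source of inflation, whose size depends on how unequal risk is between participants.

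These sizes rest on assumed feature counts, numbers of control days and simplified algorithms; they show a range of possible optimism and do not forecast this study's result. The omission itself is certain. It should be corrected, but given the exploratory purpose it does not undermine the study.

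**What to change.** Replace the cross-validation sentence in SAP 3.4.5.2 with:

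> Performance will be estimated by repeated nested cross-validation with all days of a participant in the same fold. Feature selection, across-instance imputation, tuning, threshold choice and algorithm choice are done only within the training folds. Sensitivity, specificity and AUC are computed from out-of-fold predictions, with participant-level bootstrap 95% intervals.

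Imputation is included because SAP 3.4.4 permits it across instances; its effect was not simulated. The change needs no extra participants, visits or data. It costs computing time, and the reported performance will be less favourable. SAP version 1.0 was written to protocol version 2.0 and the protocol is now at 3.0, so the wording could go into an alignment update.

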9.2.1 Study Population

The study population will be identified according to the below inclusion and exclusion criteria. For inclusion in the study, all of the following inclusion criteria must be fulfilled:

For participants with COPD:

1. Participants capable of giving signed informed consent, as described in Section 10.1, which includes compliance with the requirements and restrictions listed in the ICF and this protocol
2. Participants ≥ 40 and ≤ 80 years at baseline
3. Diagnosis of COPD stage II to IV (documented post-bronchodilator Forced Expiratory Volume in 1 second (FEV1)/ Forced Vital Capacity (FVC) < 0.7 and FEV1 $< 80\%$ predicted)
4. History of moderate or severe exacerbations (≥ 2 moderate exacerbations or ≥ 1 severe exacerbations in any 12-month time window during last 3 years prior to inclusion and ≥ 1 moderate or severe exacerbations in the last 12 months prior to inclusion, considering that the last 12 months may reflect lower exacerbation rate due to Covid-19 measures)

Company substance code **INN**
MS202559 0001

For participants in the calibration cohort:

1. Participants capable of giving signed informed consent, as described in Section 10.1, which includes compliance with the requirements and restrictions listed in the ICF and this protocol
2. Participants ≥ 40 and ≤ 80 years at baseline

Participants are not eligible for this study if they fulfill any of the following exclusion criteria:

For participants with COPD:

1. Participants who, at the discretion of the Investigator, are unlikely to complete the study or will not be able to provide reliable information for the study
2. Clinically relevant and/or serious concurrent medical conditions including, but not limited to visual problems, severe mental illness or cognitive impairment, musculoskeletal or movement disorders, cardiac disease (e.g., heart failure, arrhythmia [esp. atrial fibrillation and conduction blocks]), lung cancer (currently treated) that in the opinion of the Investigator, would interfere with participant's ability to participate in the study or draw meaningful conclusions from the study
3. Participants with a cardiac pacemaker, defibrillators, or other implanted electronic devices
4. Participants with known allergies or sensitivity to silicon or hydrogel
5. Less than 6 weeks since previous moderate/severe exacerbation

For participants in the calibration cohort:

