Covariates (status at the time of Day 0, closest record prior to):

- Demographics data at baseline: (sex, age, height, and weight, race and ethnicity)
- Body mass index will be calculated based on height and weight
- Smoking status (current, ex-, non-smoker)
- Medical history at baseline
 - Date of diagnosis of COPD
 - Number of moderate or severe exacerbations prior to baseline visit (preceding 36 months, in case available)
- Comorbidities at baseline
- Current medication including COPD treatment at baseline
- COPD severity (GOLD stage)

Lung Function and Laboratory variables

(at Day 0, moderate/severe exacerbation visit and End of study visit)

- Body plethysmography parameters: FEV1 [L], FVC [L], FEV1/FVC, TLC [L] (total lung capacity), RV [L] (residual volume), FRC_{pleth} [L] (functional reserve capacity), IC [L] (inspiratory capacity), R_{aw} [kPa s L⁻¹] (=ratio of sRaw to FRC_{pleth}; airway resistance), sR_{aw} [kPa s] (specific airway resistance), VT [L] (mean tidal volume), ERV [L] (expiratory reserve volume), IRV [L] (inspiratory reserve volume). For definitions see [Criée 2011](#).
- Blood gas analysis:(capillary) pO₂ [mmHg], O₂ saturation [%] and pCO₂ [mmHg],
- Serum CRP [mg/l] and serum procalcitonin levels [ng/ml]
- Blood count (CBC with differential); only values that are available with routine blood counts: Hb [g/dL], Hct [%], Erythrocyte count [10⁶/μL], MCV [fL], MCH [pg], MCHC [g/dL], Reticulocytes [x10³/μL] [% (of erythrocytes)], RDW [], platelet count [10³/μL], WBC count [x10³/μL], Lymphocytes [x10³/μL] [%], Monocytes [x10³/μL] [%], Neutrophils [x10³/μL] [%], Eosinophils [x10³/μL] [%], Basophils [x10³/μL] [%]

Derived and transformed data needed for the analysis are described in Section [9.7.1.1](#).

A complete mapping of objectives, outcomes and variables is available in Section [14.1.2](#).

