### 2.1.3 Lung function and laboratory values

The following variables will be measured at baseline, at each exacerbation visit, and at end of study visit.

- Current or last available body plethysmography parameters:
  - FEV1 [L],
  - FVC [L] (forced vital capacity),
  - FEV1/FVC [],
  - TLC [L] (total lung capacity),
  - RV [L] (residual volume),
  - FRCpleth [L] (functional residual capacity),
  - IC [L] (inspiratory capacity),

- Raw [kPa s L-1] (=ratio of sRaw to FRCpleth; airway resistance),
- sRaw [kPa s] (specific airway resistance),
- TV [L] (mean tidal volume),
- ERV [L] (expiratory reserve volume),
- IRV [L] (inspiratory reserve volume)
- Blood gas analysis:
  - (capillary) pO2 [mmHg]
  - O2 saturation [%]
  - pCO2 [mmHg]
- Serum CRP [mg/l] and serum procalcitonin levels [ng/ml]
- Blood count (CBC with differential):
  - Hb [g/dL]
  - Hct [%]
  - Erythrocyte count [ $10^6/\mu\text{L}$ ]
  - MCV [fL]
  - MCH [pg]
  - MCHC [g/dL]
  - Reticulocytes [ $\times 10^3/\mu\text{L}$ ] [% (of erythrocytes)]
  - RDW []
  - platelet count [ $10^3/\mu\text{L}$ ]
  - WBC count [ $\times 10^3/\mu\text{L}$ ]
  - Lymphocytes [ $\times 10^3/\mu\text{L}$ ] [%]
  - Monocytes [ $\times 10^3/\mu\text{L}$ ] [%]
  - Neutrophils [ $\times 10^3/\mu\text{L}$ ] [%]
  - Eosinophils [ $\times 10^3/\mu\text{L}$ ] [%]
  - Basophils [ $\times 10^3/\mu\text{L}$ ] [%]

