	Lung function parameters by plethysmography (see section 2.1.3, 13 parameters)	Baseline (Day 0), End of study visit
	Laboratory values (see section 2.1.3, 20 parameters): Current or last available (capillary) pO 2 , O 2 saturation and pCO 2 ; Serum CRP and serum procalcitonin levels; blood count (CBC with differential)	Baseline (Day 0), End of study visit
	Exacerbation count by mild, moderate or severe exacerbation.	End of study visit

For each pair of groups (x, y) and for each assessment time point, a table with x and y parameter groups indexing rows and columns respectively, will be provided to display coefficient of correlation and 95% CI for all parameter pairs. To provide a visualization, the tables will be plotted as matrix heatmaps displaying the correlation coefficient point estimates.

#### 3.4.5.4 Secondary Objective 4

Sensor derived data may be related to the CAT score, therefore, an additional objective is to investigate whether changes in physical activity, heart rate, heart rate variability, temperature, respiration rate, cough frequency, and sleep pattern in the 3-month observation period, are associated with changes of the patient self-assessed symptoms (CAT).

This analysis will be performed on the COPD participants set.

The following analyses will be conducted in this order:

- Linear mixed model with the patient self-assessed symptoms, CAT score, mean value assessed on a 7-day basis as the response variable and the mean values of physical activity, heart rate,

heart rate variability, temperature, respiration rate, cough frequency also assessed in the same timeframe as the independent variables. Individual trajectories will be investigated. A model including the change of each sensor variable, the time (7-day period) as fixed effect will be tested. Interaction terms between the time and each sensor variable will be included in the model and potentially patient-level random intercepts and slopes will also be included in the model. Other covariates such as age, sex, smoking status, medical history will be considered. The same model will be considered with the absolute change of the CAT score and the absolute change of the sensor variables.

$$Y_{ij} = (\alpha + a_i) + (\beta + b_i) X_{ij} + \xi_{ij}$$

where  $a_i$  is the random intercept,  $b_i$  is the random slope for the  $j^{\text{th}}$  observation of the individual  $i$

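### Objective 3b correlates sensor data, unadjusted, with nine lung volumes in absolute litres only, so these coefficients mix COPD impairment with sex, height and age

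*SAP*

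**What the plan says.** Objective 3b (Protocol 8.2 and 9.7.2.2; SAP 3.4.5.3) relates sensor data to lung function at baseline and study end. The lung-function group is "Lung function parameters by plethysmography (see section 2.1.3, 13 parameters"). For each pair, "Pearson's correlation coefficient will be computed together with a 95% asymptotic confidence interval based on Fisher's Z transform", with Kendall's Tau as an option for parameters with little variability.

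SAP 2.1.3 defines the group under "Current or last available body plethysmography parameters". Its entries carry units, for example "FVC [L] (forced vital capacity") and "TLC [L] (total lung capacity"). Protocol 9.3 gives the same parameters, starting "Body plethysmography parameters: FEV1 [L], FVC [L], FEV1/FVC, TLC [L] (total lung capacity), RV [L] (residual volume"), and Protocol 14.1.2 repeats them.

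On confounding, SAP 3.4.2 states "Not applicable. All available features will be considered in the predictive modelling" and then forces baseline covariates into the Objective 4 models only. SAP 3.4.7 plans no subgroup analysis. Percent predicted appears in the eligibility criterion, "Diagnosis of COPD stage II to IV", which requires FEV1 below 80% predicted (Protocol 9.2.1). GOLD stage is a covariate and a descriptive variable, but it is not in the Objective 3 outcome group.

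**The concern.** The study's general aim (Protocol 8) is to relate sensor data to clinical parameters for monitoring disease activity, and its entry criterion measures impairment against a predicted value. A volume in litres is the predicted volume for that person multiplied by the fraction retained, so it carries body size, sex and age as well as disease. A participant with a predicted FEV1 of 2.0 L at 75% has 1.5 L (2.0 × 0.75). So does one with a predicted 3.33 L at 45% (3.33 × 0.45).

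Two things follow for a cohort aged 40 to 80 with no restriction by sex or height. A real link between a sensor variable and impairment looks weaker than it is. And a sensor variable that differs by sex, age or height can correlate with a volume without any link to severity. A reader of the heatmaps cannot separate the two.

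**Working it through.** **1. The plan's own count.** SAP 2.1.3 lists FEV1, FVC, FEV1/FVC, TLC, RV, FRCpleth, IC, Raw, sRaw, TV, ERV and IRV. That is 12, against 13 stated in SAP 3.4.5.3. Nine are in litres (FEV1, FVC, TLC, RV, FRCpleth, IC, TV, ERV, IRV), one is a ratio and two are resistances. None is named as percent predicted.

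**2. Model for the size.** Write V = D × P, where D is the predicted volume and P the fraction of predicted, taken as independent of D.
- Var(V) = Var(D)Var(P) + Var(D)E[P]² + Var(P)E[D]²
- Dilution factor = corr(V, P) = E[D] × SD(P) / SD(V)
- For a sensor variable unrelated to P that differs by d within-sex SDs between the sexes, with a share m of men and a sex gap Δ in D: spurious |r| = m(1−m) × d × Δ × E[P] / √{[1 + m(1−m)d²] × Var(V)}

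**3. Inputs.** None of these is in the documents; all are assumptions. Men 60%. Predicted FEV1 in women 2.3 L (SD 0.35), and in men 0.5 to 1.1 L higher (SD 0.45). FEV1 uniform from a floor of 15 to 30% up to 80% predicted; eligibility sets no floor. Predicted TLC 7.0 L in men (SD 0.7) and 5.2 L in women (SD 0.6), mean 110% predicted, SD of percent predicted 10 to 25. d from 0.3 to 0.8.

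**4. Worked case, FEV1** (gap 0.8 L, range 30 to 80%). E[D] = 0.6 × 3.1 + 0.4 × 2.3 = 2.78. Var(D) = 0.6 × 0.45² + 0.4 × 0.35² + 0.24 × 0.8² = 0.324. E[P] = 0.55 and Var(P) = 0.50²/12 = 0.0208. Var(V) = 0.0068 + 0.0980 + 0.1610 = 0.266. Factor = 2.78 × 0.144 / 0.516 = 0.78, so a true 0.50 shows as 0.39.

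**5. Range.**

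| Case | Factor | True 0.50 shows as | Spurious absolute r, d = 0.3 to 0.8 |
|---|---|---|---|
| FEV1, gap 1.1 L, 30–80% | 0.74 | 0.37 | 0.07–0.19 |
| FEV1, gap 0.8 L, 30–80% | 0.78 | 0.39 | 0.06–0.15 |
| FEV1, gap 0.5 L, 15–80% | 0.89 | 0.45 | 0.03–0.08 |
| TLC, SD 10 | 0.46 | 0.23 | 0.10–0.26 |
| TLC, SD 15 | 0.61 | 0.30 | 0.09–0.23 |
| TLC, SD 25 | 0.78 | 0.39 | 0.07–0.18 |

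**6. Second route for the dilution.** If sex, height and age together explain a share R² of the litre variance, a correlation ρ with impairment alone becomes ρ√(1 − R²). For ρ = 0.50 and an assumed R² of 0.20 to 0.65, this gives 0.45 to 0.30, which overlaps the ranges above.

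**7. Precision.** With the planned 60 evaluable participants and SE 1/√57 on the Fisher scale, r = 0.15 has a 95% interval of −0.11 to 0.39 and about a 21% chance of excluding zero. For r = 0.26 the interval is 0.01 to 0.48, with about a 52% chance. An observed 0.39 has an interval of 0.15 to 0.59, which contains 0.50.

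**The case against.** The litre units are prespecified consistently in Protocol 9.3, Protocol 14.1.2 and SAP 2.1.3. The text of Objective 3b speaks of lung function, not severity. Some sensor variables, respiration rate for example, may reasonably be related to absolute tidal volume or inspiratory capacity. The study calls itself exploratory, no test or sample size rests on Objective 3, and much of the possible bias lies within sampling error at 60 participants. All of this stands. It argues for keeping the litre table. It does not make that table answer a question about severity.

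The size also depends heavily on undocumented inputs, as the table shows. That spurious r vanishes in percent predicted is built into the model, because P is independent of D.

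Three stronger readings are tempting, and the documents do not support them:
- **The study never uses percent predicted.** Eligibility does. For Objective 3 one can say only that none is named: one of the 13 stated parameters is unidentified, and the contents of the table plan are not visible. Nothing suggests that the missing parameter is a percent-predicted value. If it were, the nine litre volumes would still be unadjusted.
- **Every lung-function coefficient is distorted.** FEV1/FVC, Raw and sRaw are not litre volumes. The spurious part arises only for sensor variables that themselves differ by sex, age or height.
- **The litre values should be replaced.** They are fixed outcome variables and legitimate in themselves; an addition is enough.

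**Conclusion.** The point holds for the nine litre volumes. As planned, their Objective 3b coefficients mix impairment with sex, height and age, and nothing in the plan for this objective separates them. The direction of the dilution follows from the structure; the size rests on the assumed ranges. For FEV1 the factor is about 0.74 to 0.89, and spurious absolute r about 0.03 to 0.19. For TLC the figures are about 0.46 to 0.78 and 0.07 to 0.26. That litre volumes depend on sex, height and age is general physiology that the documents do not quantify.

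The consequence is limited to how an exploratory secondary objective is read. The primary analysis and the sample size are untouched. Because the correction is nearly free, it is worth making.

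**What to change.** Keep the prespecified litre table. In SAP 2.1.3 and 3.4.5.3, add beside it:
- percent predicted or z-scores from one named reference equation, at least for FEV1, FVC, TLC, RV and FRCpleth;
- for the other litre volumes (IC, TV, ERV, IRV), partial correlations adjusted for sex, age and height;
- a sentence saying that statements about disease severity rest on these added results.

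Also reconcile the 13 parameters stated in SAP 3.4.5.3 with the 12 listed in SAP 2.1.3.

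The cost is SAP wording and derived variables. Sex, age, height and ethnicity are already collected (SAP 2.1.1), so no new measurement or visit is needed. The downsides are a larger table and dependence on the chosen reference equation. Adjusting for three covariates costs little precision: at 60 participants the Fisher-scale SE goes from 1/√57 = 0.132 to 1/√54 = 0.136.
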